The proposed pilot study is a one-year randomized, rater- and dose-blinded trial evaluating the potential role of melatonin in subjects with relapsing multiple sclerosis who have been taking a stable dose of an oral DMT for at least 6 months. The oral DMTs include dimethyl fumarate, fingolimod, teriflunomide, diroximel fumarate, siponimod, and ozanimod. Thirty subjects with relapsing forms of multiple sclerosis who meet all of the eligibility criteria will be enrolled at Providence Neurological Specialties in Portland, Oregon. The subjects will be consented by the investigator or delegated research personnel before undergoing any study procedures. Subjects will be randomized to melatonin 3 mg, or melatonin 5 mg. There will be 15 subjects in each group. As this is a pilot study, we do not include a sample size calculation.

Urinary and serum melatonin testing will be conducted at baseline, month 3, month 6, month 12, and any early termination or unscheduled visits. Subject reported measures for the assessment of fatigue, QoL, sleep, and MS severity (MFIS, MSIS-29, PSQI, and PDDS-PS) will be administered at baseline, month 3, month 6, month 12, and any early termination or unscheduled visits. Relapses during the study will be documented and recorded. If the subject does have a relapse, they will be treated per our clinical protocol which consists of Solu-Medrol 1 gram IV once a day for 3 to 5 days depending on the severity of symptoms.

If discontinuation of oral DMT and/or melatonin occurs, the subject may continue in the trial for observational purposes. An unscheduled (UNS) visit will be completed within 7 days after the last dose of oral DMT and/or melatonin (date of whichever is stopped first, if both discontinued). They will complete all applicable visits items moving forward (urinary 6-SMT reminder, urinary 6-SMT collection, dispense 24- hour urine collection materials, serum melatonin collection, dispense subject dosing diary, dispense study drug, study medication compliance/accountability, and potentially oral DMT compliance assessment will no longer be relevant/required). If oral DMT and/or melatonin is discontinued and the subject is unwilling to stay on the study for observational purposes, an early termination visit must be performed within 7 days after the last dose date of whichever is stopped first.

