 - ii. At the discretion of the investigator for medical or ethical reasons
 - iii. If the subject withdrawals consent
 - iv. If the subject is unwilling or unable to comply with the protocol, per investigator discretion
- G. Statistical Methods

Subject characteristics for each arm will be reported for continuous variables (mean, standard deviation, median, and range) and categorical variables (counts and percentages). All analyses will use two-sided tests at the 0.05 significance level. This study is based on an intention to treat model, in which all subjects receiving at least one dose of melatonin will be included.

a. Primary Analysis

Longitudinal analyses using a linear mixed models for repeated measures will be used to compare changes in 24-hour urinary 6-sulfatoxymelatonin and serum morning Melatonin over time between arms. Each outcome will be treated as continuous and identify link functions will be used. Overall trajectories as well as the mean change from baseline to 3, 6, and 12 months for each arm will be reported and compared.

b. Secondary Analysis

Changes in the MFIS, MSIS-29, PSQI, & PDDS-PS from baseline to 3, 6, and 12 months will be reported and tested using a paired t or Wilcoxon signed-rank test for related samples. Twosample t or Mann-Whitney tests will be used to compare change between arms at each time point. The mean number of relapses during enrollment for each arm will be reported and compared using a Poisson analysis. Kaplan-Meier survival analysis methodology will be used to estimate the proportion of subjects relapse-free at months 3, 6, and 12 and log rank tests will be used to compare arms.

To examine agreement between 24-hour urinary 6-sulfatoxymelatonin and serum morning melatonin level, the measurements will be plotted and compared using prediction intervals from regression analysis as outlined in 2003 paper by J. M. Bland and D. G. Altman²⁰.

H. Regulatory

a. Regulatory Requirements

The study will be performed in accordance with ICH GCP Guidelines and the Code of Federal Regulations for clinical research. Any amendments to the study protocol must be approved by Providence Health and Services Institutional Review Board before implementation. AEs and protocol violations or deviations must be reported according to the guidelines of Providence Health and Services Institutional Review Board.

b. Safety Assessments

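### The questionnaire scales are tested visit by visit with no missing-data rule, so subjects who leave drop out of the later tests; this can make the month-12 within-arm change look too favourable

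*Combined protocol and SAP*

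**What the plan says.** The document is a combined protocol and SAP. Four parts bear on this point.

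- **Collection (section D).** The four scales "will be administered at baseline, month 3, month 6, month 12, and any early termination or unscheduled visits".
- **Population (opening of section G).** "This study is based on an intention to treat model, in which all subjects receiving at least one dose of melatonin will be included".
- **Laboratory outcomes (section G.a).** For urinary 6-SMT and serum melatonin, "Longitudinal analyses using a linear mixed models for repeated measures will be used".
- **Scales (section G.b).** Within each arm, the plan is that changes in the four scales at each of the three later visits "will be reported and tested using a paired t or Wilcoxon signed-rank test for related samples". For the doses, "Twosample t or Mann-Whitney tests will be used to compare change between arms at each time point".

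The document contains no imputation or other missing-data rule. It does not say whether scores from an early-termination (ET) or unscheduled (UNS) visit may enter the month 3, 6 or 12 comparisons.

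Two provisions limit the loss of scores. Under section D, a subject who stops the oral DMT or melatonin may stay for observation; the procedures then dropped concern urine, serum, diary and drug supply or compliance, not the questionnaires. Under section F.6, a subject who stops and will not stay has an ET visit at which the scales are completed.

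**The concern.** A paired test of change at a visit needs a baseline score and a score at that visit. A two-sample test of change needs the same from each subject. With no rule for absent scores, a subject who leaves after month 6 contributes nothing at month 12, even with baseline, month-3 and month-6 scores on file. The model in G.a can keep such a subject's partial record; the tests in G.b cannot.

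This matters most within arms. Both arms receive melatonin and there is no untreated group, so within-arm change is the plan's only evidence on whether fatigue, sleep or MS impact changes under melatonin. Section B intends the results to support a larger trial of clinical efficacy. If subjects who are getting worse are the ones who leave, those remaining look better than the whole group, and this error does not cancel. Section F.2 names relapse, adverse events, poor adherence, loss to follow-up and withdrawal among the discontinuation reasons, so a link between leaving and earlier scores is plausible. It is not established.

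**Working it through.** The plan gives no power, SD or dropout figure for these scales, so there is nothing to reproduce. What follows is an illustration.

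**Inputs.** From the document: 15 subjects per arm; visits at baseline and months 3, 6 and 12. Assumed: normal scores with SD 1 at each visit, equal correlation r = 0.5 or 0.7 between visits, true mean change zero, higher score worse, 3 of 15 per arm missing at month 12.

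**Step 1: link between month-6 and month-12 change.** Let C6 and C12 be the changes from baseline.
- Var(C6) = 2(1 - r), so the SD of change is 1.00 (r = 0.5) or 0.775 (r = 0.7).
- Cov(C6, C12) = r - r - r + 1 = 1 - r.
- The slope of C12 on C6 is (1 - r) / [2(1 - r)] = 0.5.

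**Step 2: the three worst month-6 changes leave.** The three largest of 15 standard normal values have expectations 1.736, 1.248 and 0.948, sum 3.932. All 15 sum to zero, so the 12 who stay average -3.932/12 = -0.328 SD of change. Their expected month-12 change is then:
- r = 0.5: 0.5 × (-0.328) × 1.00 = -0.16
- r = 0.7: 0.5 × (-0.328) × 0.775 = -0.13

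Simulations of 4,000 trials per setting agree: -0.17 and about -0.13 score SD. When noise weakens the selection they give -0.12 and -0.09. A likelihood estimate that also uses the earlier scores of those who left stays within 0.01 of zero.

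**Step 3: size against sampling error.** With 12 subjects the standard error of mean change is 1.00/√12 = 0.29 or 0.775/√12 = 0.22. The bias is therefore about 0.4 (0.12/0.29; 0.09/0.22) to 0.6 (0.17/0.29; 0.13/0.22) of a standard error.

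**Step 4: other dropout shares.** A large-sample simulation (400,000 subjects) let the odds of leaving after month 3 or 6 rise with observed worsening (log odds ratio 1 per SD). Bias in month-12 change, in SD of change:

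| Dropout by month 12 | Visit-wise test | All observed scores |
|---|---|---|
| 10% | about -0.05 | about 0 |
| 20% | -0.09 to -0.10 | about 0 |
| 30% | -0.14 | about 0 |

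**Step 5: where the bias vanishes or persists** (3 of 15 lost per arm).
- Random loss: zero with either method.
- Loss of those with the worst month-6 score, rather than the worst change: Cov(Y6, Y12 - Y0) = r - r = 0, so no bias in change under this correlation structure.
- Same loss pattern in both arms: the between-arm bias cancels to zero.
- Loss tied to the unseen month-12 change: visit-wise -0.33 (r = 0.5) and -0.25 (r = 0.7); likelihood estimate still -0.24 and -0.19. About three-quarters remains (0.24/0.33 = 0.73; 0.19/0.25 = 0.76).
- Unequal loss, 4 of 15 against 1 of 15, selected on month-6 change: between-arm bias about -0.12 to -0.16 under strong selection and -0.07 to -0.11 under weaker selection, against at most 0.02 with the likelihood estimate.

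**The case against.** The strongest reply has four parts.

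1. **Population.** A reader might infer that G.b contradicts the one-dose rule. The documents do not support that. The rule defines who belongs to the analysis set; it does not say how an absent score is handled. A subject lost after month 6 still enters the month-3 and month-6 tests and the relapse analyses. What stands is that the rule is not carried through to the later visits. Likewise, the plan nowhere says that only attenders are analysed; that follows from the choice of tests and the silence on missing scores.

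2. **Stopping is not leaving.** A reader might treat every discontinuation reason in F.2 as a lost score. Observational follow-up and the ET questionnaires show otherwise, and this objection stands. The problem is confined to subjects who leave or miss visits, and to ET scores that have no assigned place in the analysis.

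3. **The bias depends on the mechanism.** A reader might infer that the tests are biased as such. They are not: step 5 shows patterns with no bias, and one in which the mixed model removes only about a quarter. For the dose comparison, nothing in a dose-blinded trial of two active arms points to a fourfold difference in dropout; even then the null rejection rate was 6 to 7% instead of 5%.

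4. **The gain is small.** Under the selection in step 2, the root mean squared error of within-arm change was 0.33 visit-wise against 0.31 by likelihood (r = 0.5), and 0.25 against 0.24 (r = 0.7). Precision gains are 0 to 2%. The gain lies in bias, not power.

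These points limit the size and wording of the concern. They do not supply the missing rule or favour the visit-wise tests.

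**Conclusion.** The concern holds in a limited form. G.b tests four scales separately at each visit and has no missing-data rule, so subjects who leave drop out of later tests although earlier scores exist. The month-12 within-arm change can then look too favourable, by about 0.09 to 0.17 score SD with 3 of 15 lost per arm and correlations of 0.5 to 0.7, if loss follows earlier observed worsening. The dropout share, correlation and strength of selection are all assumptions.

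Two stronger readings are not supported: that bias is certain, and that the comparison of 3 mg with 5 mg is generally distorted. The latter needs loss, or its link to the scores, to differ by dose. Nor is a mixed model a full remedy when loss depends on scores never observed. Severity is low to moderate: these are secondary outcomes of an exploratory pilot, but the better method is already in the plan.

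**What to change.** In section G.b:

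- For MFIS, MSIS-29 and PSQI, make the repeated-measures mixed model of G.a the main analysis, with arm, visit as a category and arm-by-visit, all scheduled visits of all dosed subjects, and small-sample degrees of freedom. Take the within-arm and between-arm changes at months 3, 6 and 12 from it.
- Keep the paired and two-sample tests at each visit as a sensitivity analysis.
- Keep rank tests for PDDS-PS. They remain visit-wise, so say so when reporting them.
- State how ET and UNS scores are used, including whether they can stand for a scheduled visit.
- Report the number analysed per arm and visit for every scale.

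The cost is SAP wording and a little programming; no new data are needed. The downside is a model with more assumptions than a t-test, fitted to 30 subjects; the sensitivity analysis covers this.

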Melatonin will be provided by the study. However, oral DMT will be provided by the subject's specialty pharmacy and paid by the subject or the subject's insurance.

E. Outcome Measures

- 1. Primary Outcome
 - i. Change in urinary 6-SMT in 24 hours urine
- 2. Secondary Outcomes:
 - i. Change in Serum morning Melatonin level
 - ii. Change in MFIS

iii. Change in MSIS-29

iv. Change in PSQI

v. Number of Relapses during enrollment

vi. Change in PDDS-PS

F. Methods

- 1. Subject Selection
- a. Inclusion Criteria
 - i. Male and female subjects with relapsing forms of MS who have been on a stable dose of dimethyl fumarate, fingolimod, teriflunomide, diroximel fumarate, siponimod, or ozanimod for 6 months or longer
 - ii. Confirmed diagnosis of Relapsing MS

iii. Ages 18 to 65 who are able to provide informed consent

- iv. Women of childbearing potential must employ proven methods to prevent pregnancy during the course of the trial; the acceptable method will be left to the judgment of the investigator
- v. Not pregnant or lactating
- vi. No evidence of significant cognitive or psychiatric disorder
- vii. Able to understand the purpose and risks of the study

viii. Must be willing to sign an informed consent and follow the protocol requirements

b. Exclusion Criteria

i. Use of melatonin within 30 days of enrollment

- ii. The addition of any sleep aide or change in dose within 30 days of enrollment or during the trial
- iii. The addition or change in dose of Vitamin D within 30 days of enrollment or during the trial
- iv. Change in DMT during the trial
- v. Steroid therapy within 30 days of enrollment
- vi. Use of anticoagulation at the time of enrollment and during the trial
- vii. The addition of an antidepressant is not allowed during the study period; if on an antidepressant at screening, the dose must be stable 30 days prior to enrollment and dose changes are prohibited during the study

- viii. The addition or change in dose of any stimulants, including but not limited to, amantadine, armodafinil, methylphenidate, or modafinil within 30 days of enrollment or during the trial
- 2. Discontinuation of Subjects from the Study
 - i. Subjects may voluntarily withdraw consent and discontinue their participation in the study at any time
 - ii. If a subject has a relapse during the study, the study doctor may discontinue melatonin and/or oral DMT

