 - a. A relapse is defined as a new symptom, or worsening of pre-existing neurologic symptoms, of at least 24 hours duration, in subjects who had been clinically stable for the prior 30 days, in the absence of fever, sleep deprivation or severe emotional stress.
 - iii. Subject has an adverse event that presents unacceptable risk, per investigator discretion
 - iv. Subject has inadequate adherence to the protocol, per investigator discretion
 - v. Subject is lost to follow-up
 - vi. Subject becomes pregnant
- 3. Method of Treatment Assignment

The randomization sequence will be generated using R statistical software and will be stratified by age group and gender with a 1:1 allocation using a fixed block size of four. The following four strata will be used: 1) younger females, 2) older females, 3) younger males, and 4) older males. As subjects enter the study, they will be designated to a stratum and will be assigned either a 3 mg or 5 mg melatonin dose based on the pre-generated randomization scheme within that stratum. A master list containing drug kit numbers and drug assignment will be kept in a password-protected computer file in the research pharmacy. The investigator, study coordinator and subjects will remain blinded until study completion. The blind will only be violated if, in the judgment of the treating investigator, unblinding is necessary for subject safety.

4. Study Treatment

- i. All subjects will continue their oral DMT and start the study drug on Day 1 (Baseline Visit).
- ii. Oral DMT will be taken per standard of care dosing and paid for by the subject/subject insurance.
- iii. Subjects randomized to melatonin will take either 3mg once a day or 5mg once a day. Melatonin will be supplied by Thorne Pharmaceuticals. The study drug will be taken at 21:00 each day ±2 hours.

5. Concomitant and Excluded Therapy

The addition of a sleep aide is not allowed during the study period. If subjects were on a sleep aide prior to the trial, no change in this medication is allowed and the dose must be stable 30 days prior to enrollment.

No change in Vitamin D supplementation will be allowed during the study and the dose must be stable 30 days prior to enrollment.

The addition of an antidepressant is not allowed during the study period. If on an antidepressant at screening, the dose must be stable 30 days prior to enrollment and dose changes are prohibited during the study.

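### Relapse counts are compared between arms with no stated allowance for time in study; a person-time offset should be specified

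*Combined protocol and SAP*

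**What the plan says.** Section E lists the secondary outcome as "Number of Relapses during enrollment", a count with no time denominator. Section G.b carries this into the analysis: "The mean number of relapses during enrollment for each arm will be reported and compared using a Poisson analysis". Neither section, nor any other, mentions an offset, exposure, person-time or an annualised rate for relapses.

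The analysis set is one "in which all subjects receiving at least one dose of melatonin will be included" (Section G), so a subject who leaves early counts as a full subject in the mean.

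Follow-up can end early. Section F.2 lists withdrawal of consent, loss to follow-up and an adverse event, and lets the study doctor stop melatonin or the oral DMT after a relapse. When treatment stops, staying for observation is optional. Section D says that if "the subject is unwilling to stay on the study for observational purposes, an early termination visit must be performed within 7 days". For those who do stay, "They will complete all applicable visits items moving forward", and relapse assessment is not among the items dropped.

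The same paragraph of G.b has a second relapse analysis: "Kaplan-Meier survival analysis methodology will be used to estimate the proportion of subjects relapse-free at months 3, 6, and 12", with log-rank tests between arms.

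**The concern.** A mean count per subject estimates a relapse rate only if every subject is watched for the same time. If one arm accumulates less person-time, its mean count falls although its relapse rate is unchanged. Two analysts following the G.b sentence could also obtain different answers, one comparing counts and the other comparing rates.

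There are two ways for the count ratio to mislead. If follow-up differs between arms, by design or by chance, the ratio moves away from 1 with no true effect. If there is a true dose effect and some subjects leave after a relapse, the arm with more relapses loses more time and the ratio moves toward 1.

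The time-to-event analysis does not repair this, because it ignores second and later relapses and does not adjust the count comparison. Section B presents the pilot as a prelude to a larger trial. A rate per person-year can be carried into that planning; a mean count over unspecified time cannot.

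**Working it through.** **Inputs from the documents.** 15 subjects per arm, one year planned (Section D). The relapse definition in F.2 applies "in subjects who had been clinically stable for the prior 30 days". There is no relapse rate, dropout rate or sample size calculation, so there is no figure to reproduce.

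**Assumed inputs.** Dropout 10% to 30%; relapse rates 0.15 to 1.0 per year; where a true effect is assumed, a rate ratio of 2.0. These are illustrations, not predictions.

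**1. Equal relapse rates, unequal dropout.** The expected count ratio (higher-dropout arm over lower) equals the ratio of person-time. For 30% versus 10%:

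- all leave at month 3: (0.70 + 0.30 × 0.25) / (0.90 + 0.10 × 0.25) = 0.775 / 0.925 = 0.838
- constant hazard: [0.30 / −ln 0.70] / [0.10 / −ln 0.90] = 0.841 / 0.949 = 0.886
- exits uniform over the year: 0.85 / 0.95 = 0.895

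For 20% versus 10% the same three cases give 0.919, 0.944 and 0.947. Per person-year the ratio is 1.00 in each. With equal true dropout the expected count ratio is also 1.00.

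**2. Chance imbalance.** Same true dropout in both arms, 15 per arm, uniform exit, 400,000 simulated trials. The person-time ratio falls outside 0.90 to 1.11 in about 13%, 27% and 38% of trials at 10%, 20% and 30% dropout.

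**3. True ratio 2.0, some leaving after a relapse.** Let L be the rate while at risk, p the probability of leaving at each relapse, and g the time after a relapse when no new one can count. The at-risk probability follows a′(t) = −L a(t) + L(1−p) a(t−g). Mean count = L∫a, and the probability of being in study at t = 1 − pL∫a up to t. With g = 30/365:

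| Rates per year | p | Count ratio | Person-year ratio |
|---|---|---|---|
| 0.15 vs 0.30 | 0.25 | 1.947 | 1.983 |
| 0.3 vs 0.6 | 0.25 | 1.898 | 1.966 |
| 0.5 vs 1.0 | 0.25 | 1.838 | 1.944 |
| 0.15 vs 0.30 | 0.50 | 1.918 | 1.988 |
| 0.3 vs 0.6 | 0.50 | 1.843 | 1.977 |
| 0.5 vs 1.0 | 0.50 | 1.756 | 1.962 |

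**4. What the offset leaves behind.** The stability clock starts once the subject is stable, so the gap is at least 30 days and may be longer. With nobody leaving, the count and person-year ratios are the same: 1.977, 1.955, 1.927 at 30 days and 1.957, 1.917, 1.869 at 60 days. The offset corrects none of that. With p = 0.25, compare the log shift that the offset corrects, ln(person-year ratio / count ratio), with what remains, ln(2 / person-year ratio), from the lowest to the highest pair of rates:

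- 30 days: corrects 0.018 to 0.056, leaves 0.009 to 0.028
- 60 days (count 1.932 to 1.801, person-year 1.967 to 1.897): corrects 0.018 to 0.052, leaves 0.017 to 0.053
- 90 days (count 1.920 to 1.768, person-year 1.953 to 1.858): corrects 0.017 to 0.049, leaves 0.024 to 0.074

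If rates also vary between subjects (gamma, coefficient of variation 1, 30-day gap, p = 0.25), simulation gives count ratios of 1.90, 1.83, 1.75 and person-year ratios of 1.93, 1.89, 1.83.

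**5. Scale.** SE of the log ratio = √(1/expected count A + 1/expected count B), at full follow-up for the first two:

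- 0.15 vs 0.30: √(1/2.25 + 1/4.5) = 0.82
- 0.5 vs 1.0: √(1/7.5 + 1/15) = 0.45
- 0.15 in both arms with 14.25 and 12.75 person-years: √(1/2.1375 + 1/1.9125) = 1.00

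The 10% versus 30% dropout shift is |ln 0.895| = 0.11 to |ln 0.838| = 0.18, against about 1.0 at 0.15 per year.

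**The case against.** The strongest reply is that this is incomplete wording, not a shown error. Exposure adjustment is an ordinary part of a Poisson analysis, and the plan never says that follow-up time will be ignored. A reader might infer that the trial will compare unadjusted counts, or that the relapse comparison is biased. The documents support neither: they are silent on the offset and give no reason to expect different dropout between two blinded doses.

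A reader might also infer an inflated false-positive rate. Under assumed rates of 0.2 to 0.8 per year and dropout of 0% to 40% per arm, an exact test rejects 1.0% to 5.1% of the time without the offset and 1.0% to 3.9% with it. Any harm is to the estimate and its interpretation.

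The plan also limits the problem already. Subjects who stop treatment may stay for observation, and the log-rank test allows for censoring. At the lower assumed rates, about 2 to 5 relapses per arm, most would be first relapses.

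All of this stands as to weight. It does not remove the point: the quantity that the plan undertakes to report and compare is a mean count, observation after stopping is optional, and person-time can differ by chance in the single trial that is run.

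**Conclusion.** The point holds as a free improvement to one secondary outcome of a 30-subject pilot. Followed literally, G.b compares counts over possibly unequal time, and nothing elsewhere supplies the missing term. The distortion is conditional and modest: none on average with equal rates and equal exit, and about 5% to 16% in the count ratio if dropout differs by 10 to 20 percentage points. In every case examined it is well below the standard error. All of these sizes rest on assumed relapse rates, dropout rates and exit times.

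The offset should not be presented as a full cure. Relapse-related exit still biases the rate ratio when rates vary between subjects. The 30-day stability requirement leaves some person-time not at risk, and if that gap is long, the remaining bias can exceed what the offset corrects.

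**What to change.** In Section G.b, replace the sentence on mean relapses with text to this effect: relapses per person-year will be reported for each arm, counting all observed relapses and all time in study, including observation after treatment stops; arms will be compared by Poisson regression with log(time in study) as offset, giving a rate ratio with its confidence interval. State which dates start and end time in study. Keep Kaplan-Meier and log-rank for time to first relapse.

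Add a sentence on the limits: the offset reduces but does not fully remove bias from relapse-related exit, and the stability requirement in the relapse definition means that some counted time is not at risk.

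The cost is a few lines of text. The regression needs only each subject's relapse count and the start and end dates of follow-up, not the date of every relapse. Section D says "Relapses during the study will be documented and recorded", and censoring in the Kaplan-Meier analysis already needs end dates for subjects without a relapse. The only additions are later relapses in the count and the end date for subjects who have relapsed. No visit, treatment or sample size changes, and when follow-up is equal the rate ratio is the same as the ratio of mean counts.

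### With few relapses likely, the unspecified Poisson comparison in G.b can give opposite answers on the same data; name a conditional test with person-time and label it exploratory

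*Combined protocol and SAP*

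**What the plan says.** The number of relapses is a secondary outcome (section E). Section G.b plans two comparisons between arms. For counts: "The mean number of relapses during enrollment for each arm will be reported and compared using a Poisson analysis". For time to relapse, it plans Kaplan-Meier estimates at months 3, 6 and 12, and "log rank tests will be used to compare arms". The opening of section G adds: "All analyses will use two-sided tests at the 0.05 significance level".

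On size, section D says "There will be 15 subjects in each group", describes a one-year trial, and states that no sample size calculation was made because this is a pilot. The population is relapsing MS in subjects "who have been taking a stable dose of an oral DMT for at least 6 months".

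G.b does not state whether the Poisson p-value is Wald, likelihood-ratio, score or exact. It gives no person-time offset, no rule for an arm with no relapse, and no check for overdispersion. It does not say which of the two relapse comparisons is the main one. No expected relapse rate appears anywhere.

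**The concern.** An analyst would most naturally read G.b as a Poisson regression with arm as the covariate, and report whichever p-value the software prints. Wald and likelihood-ratio p-values both rest on large-sample theory, and thirty subjects on stable therapy for a year may have only a few relapses. If all of them fall in one arm, the regression has no finite rate ratio and the Wald p-value goes to about 1, however extreme the split. The likelihood-ratio test on the same data errs the other way and rejects too often. The published relapse result could then turn on a software default. Section B presents this pilot as the prelude to a larger efficacy trial, so an arbitrary p-value here could mislead its planning.

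Two further gaps bear on the count comparison. Subjects may withdraw or leave through an early termination visit (F.2, F.6.f), so follow-up can differ, yet mean counts are compared with no exposure term. Relapse is also assessed at the baseline visit, before the first dose that evening (F.6.b), and the outcome is defined over enrollment, so pre-dose relapses are not clearly excluded.

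**Working it through.** There is no event, rate or power figure in the documents to reproduce. The check asks how often each candidate test rejects when the arms are truly equal.

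**Inputs from the documents**
- 15 subjects per arm, one year (section D): at most about 15 person-years per arm and 30 in total.
- Two-sided 0.05 (section G).

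**Assumptions**
- Relapse rate r of 0.1, 0.2 or 0.3 per subject-year, with 0.4 as an outer case.
- Poisson counts, equal rates, full follow-up.

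**Expected relapses.** Per arm m = 15r; in total 30r = 3, 6, 9 (12 at r = 0.4).

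**Chance that exactly one arm has no relapse.** 2·e^(−m)·(1 − e^(−m)):
- r = 0.1, m = 1.5: 2 × 0.2231 × 0.7769 = 34.7%
- r = 0.2, m = 3: 2 × 0.0498 × 0.9502 = 9.5%
- r = 0.3, m = 4.5: 2 × 0.0111 × 0.9889 = 2.2%

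**Tests for counts a and b with equal person-time**
- Wald: z = ln(a/b) / √(1/a + 1/b); an empty arm is counted as not significant.
- Likelihood ratio: 2[a·ln(2a/(a+b)) + b·ln(2b/(a+b))] against chi-square, 1 df.
- Score: (a − b)²/(a + b) against chi-square, 1 df.
- Exact conditional: doubled binomial tail, a given a + b, with probability ½.
- Mid-p: as exact, with half weight on the observed split.

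**Actual type I error at nominal 5%.** Poisson tests by full enumeration over both counts; log-rank by 20,000 simulated trials per rate, with exponential time to first relapse censored at one year.

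| Test | r = 0.1 | r = 0.2 | r = 0.3 |
|---|---|---|---|
| Wald | 0.01% | 0.4% | 1.5% |
| Likelihood ratio | 8.8% | 8.8% | 7.4% |
| Score | 3.0% | 4.7% | 4.4% |
| Exact conditional | 0.2% | 1.2% | 2.0% |
| Mid-p conditional | 0.9% | 3.0% | 4.0% |
| Log-rank | 2.2% | 4.6% | 4.7% |

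At r = 0.4 the likelihood-ratio test is at 6.6% and Wald at 2.65%, so the problem shrinks but remains.

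**Worked splits**
- 6 v 0: a fitted Poisson regression gives a log rate ratio of −22.4, a standard error of about 18,000 and Wald p = 0.999. Likelihood ratio p = 0.004, score p = 0.014. Exact p = 2 × 0.5^6 = 0.031; mid-p = 0.5^6 = 0.016.
- 3 v 0: likelihood ratio p = 0.041; exact p = 2 × 0.5^3 = 0.25.

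**Matching the interval to the test.** With N v 0, the exact 95% lower limit for the rate ratio is p/(1 − p) with p = 0.025^(1/N). For mid-p, the half weight gives p = 0.05^(1/N).
- 5 v 0: mid-p = 0.5^5 = 0.031, which is significant. The exact limit uses p = 0.025^(1/5) = 0.478, giving 0.478/0.522 = 0.92, which includes 1. The mid-p limit uses p = 0.05^(1/5) = 0.549, giving 0.549/0.451 = 1.22, which agrees with the test.

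A mid-p test paired with an exact interval can therefore contradict itself at these event counts.

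**The case against.** The strongest objection is that G.b names no faulty test. An exact conditional comparison of two Poisson counts is also a Poisson analysis, so the proposed method already fits the wording. That stands: the plan leaves the choice open, and a reader should not infer that it commits to a large-sample test.

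Three stronger readings are tempting, and none is supported.
- *All large-sample tests fail, so an exact test is required.* The score test runs at 3.0% to 4.7% at these rates and returns a p-value with an empty arm. The exact test is itself well below 5%. Its merit is guaranteed control under Poisson counts and a defined answer, not a level nearer to 5%.
- *The log-rank test is equally unreliable.* Its simulated level is 2.2% to 4.7% at rates 0.1 to 0.3. It also addresses a different quantity, time to first relapse rather than all relapses, so planning both is ordinary in an exploratory study.
- *Single-digit event numbers are certain.* They follow only from an assumed rate of 0.30 or less; at 0.4, 12 relapses are expected.

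It is also fair to say that relapse is one of six secondary outcomes in a pilot with no sample size claim. Power to detect a halved rate is at most about 6% (exact) or 19% (likelihood ratio) at rates up to 0.3. That limits how much any relapse p-value can matter and supports an exploratory label. It does not justify leaving the result to a software default.

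**Conclusion.** The concern holds in a limited form. If G.b is run as an ordinary Poisson regression at an assumed 0.1 to 0.3 relapses per subject-year, the Wald p-value almost never rejects (0.01% to 1.5%) and is uninterpretable when one arm is empty. The likelihood-ratio p-value rejects about one and a half to nearly two times too often (7.4% to 8.8%). On a 6 v 0 split the two give p = 0.999 and p = 0.004. The defect is an unspecified test and a missing exposure term, in a setting where that choice decides the answer.

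The figures rest on the assumed rates, Poisson counts, equal arms and full one-year follow-up. The log-rank plan does not need correction.

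**What to change.** In G.b:
- Report relapses per person-year by arm, counting relapses with onset after the first dose.
- Compare arms by the conditional (binomial) test given each arm's person-time. State in advance whether it is exact or mid-p, and give a confidence interval for the rate ratio of the same type.
- Name this the main relapse comparison and label it exploratory.
- Keep the Kaplan-Meier estimates and log-rank test as supportive.

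The change is SAP wording only, with no new data. The price is conservatism with few events: actual level 0.2% to 2.0% for exact and 0.9% to 4.0% for mid-p at rates 0.1 to 0.3. Mid-p does not guarantee the level. Neither version corrects for overdispersion: with negative binomial counts at rate 0.3 and dispersion 2, the exact test rejects in about 6.3% of simulated null trials and the likelihood-ratio test in about 15%. The SAP should state that limitation.
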